8.2.2. Primary Analysis of the Primary Endpoint

The primary analysis will be evaluated independently within each arm (defined by stage, age, cohort, vaccine, and IS treatment plan) in the vaccinated population. The proportion of participants meeting a protective antibody response criteria will be reported in each arm with 90% Clopper-Pearson confidence intervals and analyzed using a one-sided exact test with alpha = 0.05 against the null hypothesis that the probability of achieving a protective immune response is ≤ 0.25 . P-values will not be adjusted for multiple comparisons.

The primary analysis will be conducted in all participants with a Roche Elecsys® Anti-SARS-CoV-2 S result ≤ 200 U/mL at the Screening visit, and in the subgroup of participants with a Roche Elecsys® Anti-SARS-CoV-2 S result ≤ 50 U/mL at the Screening visit. Each analysis will occur after the evaluable participants assigned to that arm have completed the Week 4 study visit or are withdrawn from the study.

8.2.3. Sensitivity Analyses of the Primary Analysis

A sensitivity analysis will be performed on the per protocol population.

8.2.4. Secondary Analyses of the Primary Endpoint

Descriptive statistics will be used to summarize antibody response to the additional homologous vaccine dose on a continuous scale, including median, minimum, and maximum, interquartile range, geometric mean, CV of the geometric mean, and 95% confidence intervals. Summary statistics, including 25th percentile, mean, median, and 75th percentile, will be plotted for each visit by treatment arm. Geometric mean and CV of the geometric mean will be computed as follows:

$$\text{Geometric mean} = \exp(\text{mean on } \log_e \text{ scale}).$$

$$\% \text{CV geometric mean} = \sqrt{\exp((SD \text{ on } \log_e \text{ scale})^2) - 1} \times 100$$

Primary and secondary analyses will be repeated for the RBD proteins to summarize antibody response to the additional homologous vaccine dose on a continuous scale. Supportive analyses will use descriptive statistics to summarize N protein levels as evidence of COVID infection.

In the final analysis, supportive analyses will also use a multivariable regression model on the entire vaccinated population in order to estimate the rates of vaccine response within and across arms (age group, cohort, vaccine, and IS treatment plan group) using the logistic link function, and including baseline covariates for disease type (SLE, RA, MS, SSc, and pemphigus in adults

and JIA, pediatric SLE, JDM, and POMS in pediatrics) and immune response to the initial COVID-19 vaccine regimen (anti-COVID-19 antibody negative or positive).

Estimates of the average antibody response and variance within and across cohorts will be obtained from a multivariate general linear regression model. Based on published data on the assays, it is anticipated that log-transformation of assay values will allow for Gaussian assumptions to hold, but alternative Box-Cox transformations of the data may be explored to stabilize the variance.

The primary and supportive analyses will also be replicated on the Per protocol population and using alternative strategies for missing data. Additional analysis details will be provided in subsequent versions of the SAP.

8.3. Secondary Endpoints

8.3.1. Seroconversion at Week 4

Seroconversion at Week 4, following additional doses of COVID-19 vaccine, will be assessed in the subgroup of participants in the vaccinated population that are anti-COVID-19 antibody negative at Week 0. Seroconversion will be assessed separately with (a) the NIAID-VRC MSD 3 plex assay and (b) the Roche Elecsys® Anti-SARS-CoV-2 S electrochemiluminescence immunoassay.

The subgroup of participants that are anti-COVID-19 antibody negative at Week 0 will be defined as having a result less than or equal to the positive threshold value listed below at the Week 0/Baseline visit.

Seroconversion will be defined as a having a result greater than the positive threshold value listed below at the Week 4 visit. Seroconversion will be defined in a similar fashion for subsequent follow-up visits through Week 48 as well. Participants with missing anti-COVID-19 antibody response data will be considered to be MCAR.

The following positive thresholds will be used:

Assay	Test	Positive Threshold
NIAID-VRC MSD 3 plex	Wu-1 full-length spike	1,204.71 AU/mL
NIAID-VRC MSD 3 plex	RBD	517.86 AU/mL
Roche Elecsys® Anti-SARS-CoV-2 S electrochemiluminescence immunoassay	COVID-19 Spike Domain Antibody	0.79 U/mL

The proportions who seroconvert within arms will be summarized using 95% Clopper-Pearson confidence intervals in preliminary analyses. In the final analysis, comparisons of rates of seroconversion across arms and subgroups will use a two-sample Binomial exact test with nominal two-sided alpha = 0.05.

Supportive analyses will evaluate seroconversion of N protein levels in the NIAID-VRC MSD 3 plex assay (Threshold = 9,779.62 AU/ml) as evidence of COVID infection.

8.3.2. Fold Increase in anti-COVID-19 Antibody Levels at Week 4

Fold increase in anti-COVID-19 antibody levels will be assessed for the subgroups of participants in the vaccinated population that are anti-COVID-19 antibody positive at Week 0 using separately (a) the NIAID-VRC MSD 3 plex assay and (b) the Roche Elecsys® Anti-SARS-CoV-2 S electrochemiluminescence immunoassay.

The subgroup of participants that are anti-COVID-19 antibody positive at Week 0 will be defined as having a result greater than the positive threshold value listed below at the Week 0/Baseline visit.

The following positive thresholds will be used:

Assay	Test	Positive Threshold
NIAID-VRC MSD 3 plex	Wu-1 full-length spike	1,204.71 AU/mL
NIAID-VRC MSD 3 plex	RBD	517.86 AU/mL
Roche Elecsys® Anti-SARS-CoV-2 S electrochemiluminescence immunoassay	COVID-19 Spike Domain Antibody	0.79 U/mL

Participants with missing anti-COVID-19 antibody response data will not be imputed.

Fold improvement for each assay will be defined as follows and will be defined in a similar fashion for subsequent follow-up visits through Week 48 as well:

$$\text{Fold improvement} = \frac{\text{anti-COVID-19 Antibody Response}_{\text{Week 4}}}{\text{anti-COVID-19 Antibody Response}_{\text{Baseline}}}$$

Descriptive statistics will be used to summarize fold increase in anti-COVID-19 antibody levels at Week 4, including median, minimum, and maximum, geometric mean, CV of the geometric mean, and 95% confidence intervals.

Supportive analyses will evaluate fold increase in N protein levels in the NIAID-VRC MSD 3 plex assay (Threshold = 9,779.62 AU/ml) as evidence of COVID infection.

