13.3 Measures to Minimize Bias

Participants will be assigned to cohorts defined by IS medication (Cohort A and D: MMF/MPA; Cohort B and E: MTX; and Cohort C and F: BCDT) and by the initial COVID-19 vaccine regimen received (Moderna COVID-19 Vaccine, Pfizer-BioNTech COVID-19 Vaccine, or Janssen COVID-19 Vaccine). In Adult Stage 1 and the pediatric portion of the study, participants in Cohort C will be allocated to continue taking their prescribed IS medications throughout the trial. Participants in Cohort A and B will be randomized in a balanced fashion (1:1), within the cohorts defined by IS medication and initial COVID-19 vaccine regimen, to one of the available IS medication treatment plans (continue IS vs. withhold IS). Randomization will be performed using a permuted block design stratified by disease type.

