13.4.4 Analyses of Secondary and Other Endpoint(s)

For Stage 1, the multivariable logistic and linear regression models defined in Section 13.4.3 Supportive Analyses of the Primary Endpoint above will be used to compare response to additional homologous doses of COVID-19 vaccine for a variety of subgroups. Appropriate contrasts will be defined to compare vaccine response for the following:

- Continuing versus withholding IS medications will be compared within cohort (cohorts A and B only) and within and across type of vaccine.
- The types of additional vaccine dose administered will be compared within cohorts and across cohorts, and within and across IS treatment plan groups.
- Type of IS medications will be compared within and across each type of vaccine.
- Age groups and type of disease will be compared within and across each type of vaccine.
- Corticosteroid dose at baseline will be added as a covariate to the model to assess impact on vaccine response.
- Immune response to the initial COVID-19 vaccine regimen will be assessed within and across each type of vaccine.
- Additional covariates for disease activity, co-morbid illness, age, and sex may be added to assess whether the clinical parameters are associated with response to additional vaccine dose.

Data for the Moderna COVID-19 Vaccine and Pfizer-BioNTech COVID-19 Vaccine may be combined in the comparisons above to assess the effect of mRNA vaccines together.

The incidence of seroconversion following additional vaccine doses of COVID-19 vaccine will be evaluated in the subgroups of participants that are anti-COVID-19 antibody negative at baseline using separately, (a) NIAID-VRC MSD 3 plex (Wu-1 full-length spike, RBD, and N proteins) assay with thresholds <1204.7 , 517.9 , and 9779.6 AU/mL, respectively, and (b) the Roche Elecsys® Anti-SARS-CoV-2 S electrochemiluminescence immunoassay with a threshold <0.80 U/mL. The proportions who seroconvert within and across arms will be summarized using 95% Clopper-Pearson confidence intervals, and comparisons will use a two-sample Binomial exact test with nominal two-sided alpha = 0.05.

For the subgroups of participants that are anti-COVID-19 antibody positive at baseline using separately, (a) the NIAID-VRC MSD 3 plex (Wu-1 full-length spike, RBD, and N proteins) assay, and (b) the Roche Elecsys® Anti-SARS-CoV-2 S electrochemiluminescence immunoassay with a threshold ≥ 0.80 U/mL. Fold improvement for each assay will be defined as:

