13.7 Sample Size Considerations

Early reports show that a significant number of individuals taking IS medications respond poorly or not at all to COVID-19 vaccination. Ruddy et al. reported 26% of chronic inflammatory rheumatic disease patients had undetectable SARS-CoV-2 antibody response after their first mRNA vaccine dose, but many seroconverted with the second dose such that only 6% had persistent undetectable SARS-CoV-2 RBD antibodies [16]. However, those taking MMF or rituximab were at much higher risk of not mounting a detectable antibody response (89% and 67%, respectively)[17]. Another report has demonstrated diminished overall serologic response in adults with chronic inflammatory diseases, particularly in those treated with B-cell depletion or antimetabolites including MTX, with a 50-fold and 3-fold reduction in post-vaccine antibody titers relative to immunocompetent controls[80].

Based on the emerging evidence in individuals taking IS medications, an ineffective rate of achieving a protective immune response after the additional vaccine dose was defined to be less than or equal to 0.25 (null hypothesis). The study is powered to reject the null hypothesis in each arm when the true response rate is 0.5 or greater as preliminary evidence the additional vaccine dose is effective in specific study population.

The proportion of participants in each arm (cohort, additional vaccine dose, and IS treatment plan group) to receive an additional vaccine dose and achieve a protective antibody response at Week 4 will be evaluated using a one-sided exact test with alpha = 0.05 to test against a null hypothesis that the true response rate is ≤ 0.25 . A sample size of 33 evaluable participants achieves at least 90% power to reject null hypothesis when the true response rate is 0.5 or greater.

Secondary analyses will compare the rate of achieving a protective immune response across arms using the multivariable logistic regression model. For comparisons of single arms, 33 evaluable participants per arm will provide 80% power to detect an odds ratio of 4.2 when the null hypothesis is true in one arm (improvement from 0.25 to 0.584). For comparisons that combine arms, pooling 3 arms (e.g., type of additional vaccine dose) will provide 80% power to detect an odds ratio of 2.3 (improvement to 0.394).

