7.2. Randomization and Allocation

When employed in any population, randomization will be accomplished through a password-protected, web-based randomization system. The investigators, clinic personnel, and participants will not be blinded to randomized treatment assignments. Statistical and project staff at the Statistical and Clinical Coordinating Center (SACCC) and the DAIT Medical Monitor and Project Manager will be unblinded to individual treatment assignments as well. Laboratories performing assays for this protocol will be blinded to the identity and group assignment of biological materials to be studied.

7.2.1. Adult Stage 1

Participants who sign the informed consent form and meet all eligibility criteria for Stage 1 will be assigned to cohorts defined by IS medication and by the initial COVID-19 vaccine regimen received. Participants in Cohort C will be allocated to continuing to take their prescribed IS medications throughout the trial. Participants in Cohorts A and B will be randomized in a balanced fashion (1:1), within the cohorts defined by IS medication and initial COVID-19 vaccine regimen, to one of the available IS medication treatment plans (continue cohort-defining IS vs. withhold cohort-defining IS). Randomization will be performed using a permuted block design stratified by disease type.

A total of 60 participants with a Roche Elecsys® Anti-SARS-CoV-2 S result ≤ 200 U/mL will be randomized or allocated to each arm. In each arm, the number of participants with Roche Elecsys® Anti-SARS-CoV-2 S results ≤ 50 U/mL will be capped at 40 participants, and the number of participants with Roche Elecsys® Anti-SARS-CoV-2 S results >50 U/mL and ≤ 200 U/mL will be capped at 40 participants.

7.2.2. Adult Stage 2

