Participants who have signed the informed consent form and meet all eligibility criteria for Stage 2 will be allocated to cohorts defined by IS medication and by the initial COVID-19 vaccine regimen received. Participants who received either the Moderna COVID-19 Vaccine or Pfizer-BioNTech COVID-19 Vaccine will be allocated to the Stage 2 Arm that corresponds to their choice of either the Janssen vector-based COVID-19 vaccine or the other mRNA COVID-19 vaccine. Participants who received the Janssen COVID-19 Vaccine will be allocated to the Stage 2 Arm that corresponds to the Moderna COVID-19 Vaccine. Participants in Cohort D will withhold their MMF/MPA, participants in Cohort E will withhold their MTX, and any participants in Cohort F (B cell depletion therapy) who are also taking MMF/MPA or MTX will withhold these medications. No randomization will be employed.

A total of 60 participants with a Roche Elecsys® Anti-SARS-CoV-2 S result ≤ 200 U/mL will be allocated to each arm. In each arm, the number of participants with Roche Elecsys® Anti-SARS-CoV-2 S results ≤ 50 U/mL will be capped at 40 participants, and the number of participants with Roche Elecsys® Anti-SARS-CoV-2 S results > 50 U/mL and ≤ 200 U/mL will be capped at 40 participants.

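### Seroconversion comparisons ignore the randomisation strata and have no adjusted analysis: conservative for continue v withhold, open to case-mix confounding for non-randomised contrasts

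*SAP*

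**What the plan says.** SAP 8.3.1 gives per-arm seroconversion proportions with 95% Clopper-Pearson intervals. For the final analysis it adds that "comparisons of rates of seroconversion across arms and subgroups will use a two-sample Binomial exact test with nominal two-sided alpha = 0.05". Protocol 13.4.4 has the same rule: "comparisons will use a two-sample Binomial exact test with nominal two-sided alpha = 0.05". Neither document names strata or covariates for this endpoint. The endpoint "will be assessed in the subgroup of participants in the vaccinated population that are anti-COVID-19 antibody negative at Week 0". The size of that subgroup is not stated.

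On allocation, SAP 7.2.1 has Stage 1 Cohorts A and B "randomized in a balanced fashion (1:1), within the cohorts defined by IS medication and initial COVID-19 vaccine regimen", to continue or withhold the IS drug. Protocol 13.3 adds: "Randomization will be performed using a permuted block design stratified by disease type". Cohort C is allocated, not randomised. For Adult Stage 2, SAP 7.2.2 states: "No randomization will be employed". Protocol 3.5.2 says the same for Pediatric Stage 2.

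An adjusted analysis does exist, but for another endpoint. Protocol 13.4.3 and SAP 8.2.4 plan a logistic model of vaccine response with arm factors, disease type and prior antibody status. Protocol 13.4.4 takes the continue v withhold contrast from that model. Neither document applies it to seroconversion. SAP 8.1.4 classes all secondary analyses as exploratory, with descriptive p-values.

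**The concern.** The analysis of a named secondary endpoint omits the factor on which participants were block-randomised. Two consequences follow, and they differ by type of comparison.

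- **Randomised contrast (continue v withhold).** If seroconversion differs by disease, a pooled test uses a variance that includes between-disease spread, which stratified allocation has largely removed from the comparison. The test then rejects less often than it could.
- **Non-randomised contrasts (vaccine, IS cohort, disease, all of Stage 2).** Groups may differ in case mix. An unadjusted test can then show a difference that reflects who is in each group and not the factor compared.

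At stake is whether the seroconversion p-values can be read at face value, and whether a real effect of withholding in antibody-negative participants would be seen.

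**Working it through.** **1. The plan's own power figure.** Protocol 13.7 states that "33 evaluable participants per arm will provide 80% power to detect an odds ratio of 4.2", with rates 0.25 and 0.584. That sentence concerns the logistic model for protective response, so it serves here only as a benchmark. Two-sided normal approximation, n = 33, pooled rate 0.417:

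- difference = 0.334
- null standard error = sqrt(2 × 0.417 × 0.583 / 33) = 0.1214
- alternative standard error = sqrt((0.25 × 0.75 + 0.584 × 0.416) / 33) = 0.1142
- z = (0.334 − 1.96 × 0.1214) / 0.1142 = 0.84, so power = 0.800

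The stated 80% reproduces. Fisher's exact test on the same inputs has power 0.751, and actual type I error 0.0245 at a rate of 0.25. The documents do not say which two-sample exact test is meant; Fisher's is assumed throughout.

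**2. Why ignoring strata is conservative.** With arms balanced within disease, the relevant variance per person is the mean of p(1−p) over diseases, while the pooled test uses p̄(1−p̄). With five strata of 7, 7, 7, 6 and 6 per arm (assumed):

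- rates 0.10, 0.20, 0.25, 0.30, 0.40: p̄(1−p̄) = 0.184, mean p(1−p) = 0.175, ratio 1.06
- rates 0.03, 0.08, 0.20, 0.40, 0.60: p̄(1−p̄) = 0.186, mean p(1−p) = 0.143, ratio 1.30

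So the loss is small unless diseases differ a great deal.

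**3. One arm pair, 33 per arm, common odds ratio 4.2** (20,000 simulated trials per row, Monte Carlo standard error at most 0.4 points; rates by disease assumed). Size is the rejection rate with no effect.

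| Disease effect | Pooled exact | Stratified exact | Change | Size, pooled / stratified |
|---|---|---|---|---|
| None (0.25 throughout) | 0.748 | 0.736 | −1 point | 0.025 / 0.026 |
| Moderate (0.10–0.40) | 0.674 | 0.682 | +1 point | 0.020 / 0.026 |
| Strong (0.03–0.60) | 0.405 | 0.530 | +12 points | 0.011 / 0.023 |

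A second setting (four equal strata, control rates 0.15–0.60, 40 per side, odds ratio 4) gives 70% pooled and 73% stratified, or +3 points. A stratified Cochran-Mantel-Haenszel (CMH) test gives 0.801, 0.767 and 0.641 in the three rows of the table. With little disease effect that advantage comes from leaving the exact test, not from stratifying: an unstratified Pearson test gives 0.825 and 0.765 in the first two rows.

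**4. Four cohort-by-vaccine cells pooled, 33 per arm in each, odds ratio 2.3** (4,000 trials, assumed rates). Equal rates: 0.860 pooled, 0.858 stratified by cell. Rates 0.10–0.40: 0.784 and 0.812. Rates 0.05–0.60: 0.564 and 0.719.

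**5. Stratifying too finely.** The full cross in adults is 2 cohorts × 2 mRNA vaccines × 5 diseases = 20 cells. With an assumed disease mix of 40/25/15/12/8%, odds ratio 4 and no forced balance within cells, the pooled exact test compares with the 20-cell exact test as follows:

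| Per side | No disease effect | Moderate (0.15–0.40) | Strong (0.05–0.60) |
|---|---|---|---|
| 40 | 79% v 69% | 73% v 65% | 51% v 51% |
| 20 | 42% v 28% | 38% v 23% | 24% v 15% |

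The full cross therefore loses power in sparse data. Stratifying by the five diseases alone costs about one point at most in comparable settings, and gains 3 to 13 points when disease is prognostic.

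**6. Non-randomised comparisons.** Assume two strata with seroconversion 20% and 60%, no difference within strata, and 60 per side.

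- Mix 65/35 v 35/65: expected pooled rates are 0.65 × 0.20 + 0.35 × 0.60 = 0.34 and 0.35 × 0.20 + 0.65 × 0.60 = 0.46. The pooled test rejects in about 19% of trials.
- Mix 70/30 v 30/70: expected rates are 0.32 and 0.48. It rejects in about 35%.
- The stratified exact test rejects in 4% to 5% in both cases.

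**The case against.** The case for leaving the plan alone has real content.

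- **The test is valid where it matters most.** A reader might infer that ignoring the strata makes the continue v withhold p-value wrong. It does not: simulated size was 0.011 to 0.025 against a nominal 0.05. This stands.
- **A power loss is not established.** A reader might infer that power is certainly wasted. The documents give no seroconversion rates by disease. The evidence cited in Protocol 13.7 concerns drug classes, not diseases within one drug cohort, and B-cell depletion (Cohort C) is outside the randomised contrast. This stands, so the gain is given only as a range.
- **The text does not pool everything into one table.** It speaks of comparisons across arms and subgroups. A single pair such as A1 v A4 already fixes cohort and vaccine, leaving only disease unadjusted. This stands.
- **Continue v withhold is not left without adjustment overall.** For protective response it has the disease-adjusted model. The gap is confined to seroconversion.
- **Stratifying can hurt.** Antibody-negative status is fixed at Week 0, after randomisation, so balance within strata is not guaranteed in the subgroup. As step 5 shows, the 20-cell exact test loses power there. This limits how the fix may be written, but does not remove the case for stratifying by disease.
- **The endpoint is exploratory and the SAP unfinished.** SAP 8.5 defers subgroup details to later versions. This lowers the priority. It does not answer the confounding point: descriptive p-values that mix case mix with effect still mislead, and the present text commits to the unadjusted test.

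**Conclusion.** The point holds in a limited form. The seroconversion comparisons are unstratified, the randomised part of the design is stratified by disease within cohort and vaccine, and no adjusted seroconversion analysis is planned.

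For continue v withhold, the stated test is valid and conservative. Like for like, a disease-stratified exact test changes power by about −1 to +3 points if disease matters little or moderately, and by about +12 if it matters strongly. For the non-randomised contrasts, adjustment matters more: plausible imbalance can produce differences with no effect behind them, although the 19% and 35% above illustrate assumed mixes and do not predict this trial.

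These sizes rest on assumed stratum rates, a common odds ratio, the stated subgroup sizes and Fisher's test as the exact test. Priority is minor to moderate.

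**What to change.** In SAP 8.3.1, and in Protocol 13.4.4 when next amended:

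1. **Within an arm pair**, compare continue v withhold with an exact conditional test and an odds ratio, both stratified by disease type. Name the exact test.
2. **When arms are pooled**, also account for IS cohort and vaccine, but do not use the full cohort × vaccine × disease cross in sparse data. Either state in advance how sparse strata are merged, or add seroconversion to the logistic model of Protocol 13.4.3 with these factors as main effects.
3. **For non-randomised comparisons** (vaccine, IS cohort, disease, Stage 2), use the Protocol 13.4.3 covariates, omitting prior antibody status where the antibody-negative subgroup already fixes it. Say that such adjustment covers measured factors only.
4. **Keep** the per-arm Clopper-Pearson intervals.

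The cost is SAP wording, a little more programming and about one point of power if disease turns out not to be prognostic. No new data are needed: the factors are already recorded. SAP Section 2 provides for updates before database lock, so the change fits the existing process.
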